Endpoints:	
Primary Endpoint: The primary endpoint will be the enumeration of Mtb antigen-specific CD4+ and CD8+ T cell populations in the airway and peripheral blood at early and late time points after bronchoscopic Tuberculin Purified Protein Derivative (PPD) instillation.
 
Secondary Endpoint: The secondary endpoint will be the quantification of [¹⁸F]fluoro-D-glucose (FDG) uptake in adjacent pulmonary parenchyma and draining thoracic lymph nodes via PET-CT at early and late time points after PPD instillation.
 
Exploratory Endpoints: (a) An exploratory endpoint will be the quantification of frequencies of cell surface molecules, intracellular cytokines and transcription factors among immune cell populations in the airways vs circulation following bronchoscopic instillation of Tuberculin Purified Protein Derivative (PPD) into the lungs of individuals with or without LTBI. (b) An exploratory endpoint will involve the identification and quantification of soluble mediators in the airway and peripheral blood after PPD instillation in the lungs within the same context.

Study Population:	
Up to 100 male and female subjects will be screened in order to generate a Sample size: 13 confirmed latent tuberculosis infection (LTBI) cases and 7 confirmed non-LTBI controls
 
Gender: male or female
 
Age: 18 – 64 years of age
 
Demographic group: no exclusions

Abbreviated Title: Tissue-Specific Immune Responses to Tuberculin Purified Protein Derivative (PPD) in the Human Lung **Version Date:** 12/17/2024

[figure not shown]
Phase:	General health status: healthy volunteers (non-LTBI controls vs confirmed LTBI)
Description of Sites/Facilities	Not applicable
Enrolling Participants:	NIH Clinical Center: Procedures, Vascular Access and Conscious Sedation (PVCS) suite, Building 10; Radiology and Imaging Sciences Suite, Building 10; Laboratories of [name] and [name], Building 33
Description of Study Intervention:	Bronchoscopic instillation of 0.5 tuberculin units (10 microliters) of Tuberculin Purified Protein Derivative (PPD)(TUBERSOL®, Sanofi Pasteur Inc., Swiftwater, PA) diluted in 10 cc normal saline into the anterior segment of the right upper lobe.
Study Duration:	5 years
Participant Duration:	30 days

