1.3 SCHEDULE OF ACTIVITIES (SOA)

Schedule of Activities (SOA) AND ASSESSMENTS	EVALUATION	Screen*	Baseline						Study Visits 3 to 6			Telephone Follow- up Day 30
PROTOCOL TIMEPOINT			V1	V2	V3	V4**		V5	V6**			
Window +/- days	-60 Days	-7 Days			-2 /+3 D				-5 /+6D			
day /month				D0	D4	D5	D20	D21				
Assessments												
Review Inclusion/Exclusion Criteria	X											
Consent to study	X											
Review Medical History with Mtb Exposure		X ¹										
Review of Medications	X	X	X	X	X	X	X	X	X			
Physical Examination	X	X	X	X	X	X	X	X	X			
Weight, Height, and BMI	X											
Vital Signs (BP, HR, Resp, Temp O ₂ Saturation)	X	X	X			X			X			
Adverse Event Review			X	X	X	X	X	X	X		X	
CHEMISTRY LABS												
Female, Pregnancy Test (blood or urine) ²	X	X	X	X	X	X	X	X	X			
Acute Care Panel	X	X		X					X			
Mineral Panel	X	X		X				X			X	
CRP	X	X		X			X		X			
Hepatic Panel	X	X			X			X				
LDH	X	X		X			X		X			
International Normalized Ratio (INR), Prothrombin Time (PT), and Partial Thromboplastin Time PTT		X ³	X ³		X ³			X ³				
COVID-19 (PCR)	X											
HEMATOLOGY LABS												
CBC with differential	X	X		X			X		X			
ESR	X	X		X			X		X			
Viral Serologies												
Hepatitis B, C	X											
HIV	X											
Additional Tests												
*QuantiFERON Gold Test (IGRA)	X									X		
*Tuberculin skin test (TST)	X ⁴											
EVALUATIONS												
EKG	X		X		X			X		X		
*Chest X-RAY	X											
Chest PET-CT			X		X			X				
PROCEDURES												
Bronchoscopy					X ³			X ³		X ³		

STUDY MEDICATION							
Installation of Tuberculin Purified Protein Derivative (PPD) and saline			X				
Removal of Tuberculin Purified Protein Derivative (PPD) and saline cells				X		X	
Research Samples							
Immunology Assays = 40 mL via heparinized green top tubes			X	X		X	

* = Medical history screening activities may be done utilizing the Telehealth Visit Platform. Screening tests may be used as baseline if performed within 60 days. If re-screened after 60 days, the TST, IGRA, & chest x-ray will not be repeated unless there is a known tuberculosis exposure, including but not limited to travel to an endemic area or direct contact with an individual with known or suspected tuberculosis disease.

x¹ = History of exposure to persons with active TB; History of residence in a TB-endemic country and Estimate of time when LTBI most likely occurred

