8.3 SAFETY AND OTHER ASSESSMENTS

First participants will undergo history and physical assessment, blood or urine pregnancy test and a confirmatory TB skin test, and have blood drawn for an interferon gamma release assay (IGRA; Quantiferon Gold In-Tube, Qiagen) screening. Subjects will undergo a chest x-ray (CXR) to rule out for active disease. This is to ensure their eligibility prior to undergoing PET/CT scans, and bronchoscopies.

Eligible study subjects will be given a username and password to access a web-based patient self-reporting diary to record any evidence of self-assessed adverse events. At each study visit this will be reviewed with the subject by a designated research study personnel. If a subject reports a possible serious adverse event, then the subject will be contacted immediately for review of event(s) by designated research study personnel. Subjects will also be directed to contact research study nurse if they have any concerns or questions.

Biological specimen collection and laboratory evaluations.

Bronchoscopy, BAL and Bronchoscopic Instillation

Study subjects will undergo three bronchoscopies and bronchoalveolar lavages for the evaluation of airway and alveolar immune cells.

The study subject will be required to be without solid food or drink after midnight or six hours prior to each bronchoscopy.

First, topical anesthesia will be achieved via administration of inhaled medications containing lidocaine. Following completion of local anesthesia, sedative medications will be administered to achieve a level of moderate sedation.

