8.4.4 Time Period and Frequency for Event Assessment and Follow-Up

The occurrence of an adverse event (AE) or serious adverse event (SAE) may come to the attention of study personnel during study visits and interviews of a study participant presenting for medical care, or upon review by a study monitor.

All AEs including clinically significant laboratory tests, local and systemic reactions not meeting the criteria for SAEs will be captured on the appropriate case report form (CRF). Information to be collected includes event description, time of onset, clinician’s assessment of severity, relationship to study product/research procedure (assessed only by those with the training and authority to make a diagnosis), and time of resolution/stabilization of the event. All AEs occurring while on study must be documented appropriately regardless of relationship. All AEs will be followed to adequate resolution.

Any medical condition that is present at the time that the participant is screened will be considered as baseline and not reported as an AE. However, if the study participant's condition deteriorates at any time during the study, it will be recorded as an AE.

Changes in the severity of an AE will be documented to allow an assessment of the duration of the event at each level of severity to be performed. AEs characterized as intermittent require documentation of onset and duration of each episode.

The principal investigator will record all reportable events with start dates occurring any time after informed consent is obtained until 7 (for non-serious AEs) or 30 days (for SAEs) after the last day of study research procedure or until resolution or stabilization of an SAE whichever comes later. At each study visit, the investigator will inquire about the occurrence of AE/SAEs since the last visit. Events will be followed for outcome information until resolution or stabilization via in person, telephone and or e-mail.

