9.2 SAMPLE SIZE DETERMINATION

This is a pilot study which will be hypothesis-generating in nature. For this reason we will not be pursuing the formal sample size calculation that corresponds to a specified statistical power. However, the sample size of 13 confirmed LTBI cases and 7 confirmed non-LTBI controls (a total of 20 subjects) is slightly larger than those of the original studies of the current bronchoscopic instillation model pioneered by Silver and colleagues (21-23). Silver's 2003, 2005 and 2011 PPD bronchoscopic instillation studies included a total of 9, 15, and 14 total subjects respectively. Each study was able to demonstrate a statistically significant increase in the frequency of Mtb-specific CD4+ T cells in the BAL of LTBI subjects as compared to the BAL of non-LTBI controls within each study. Furthermore, we anticipate that our immunological signals will likely stand out due to confirmation of LTBI status using concordant TST and IGRA testing. We will enroll up to an additional 5 subjects in order to achieve 20 completed studies.

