10.2 STUDY DISCONTINUATION AND CLOSURE

This study may be temporarily suspended or prematurely terminated if there is sufficient reasonable cause. Written notification, documenting the reason for study suspension or termination, will be provided by the suspending or terminating party to study participants. If the study is prematurely terminated or suspended, the Principal Investigator (PI) will promptly inform study participants, the Institutional Review Board (IRB), and sponsor and will provide the reason(s) for the termination or suspension. Study participants will be contacted, as applicable, and be informed of changes to study visit schedule.

Circumstances that may warrant termination or suspension include, but are not limited to:

- Determination of unexpected, significant, or unacceptable risk to participants
 - a. A single SAE in a subject that is assessed as related or possibly related to the study drug
 - b. Grade 3 or higher laboratory abnormality in 3 or more subjects with a reasonable possibility of a causal relationship to the administration of study drug
 - c. Grade 3 or higher with the same or similar Adverse Event in 2 or more subjects assessed as possibly related to study drug.
 - d. Will restart study if investigation determines study drug not to be the cause
- Insufficient compliance to protocol requirements
- Data that are not sufficiently complete and/or evaluable
- Determination that the primary endpoint has been met

Study may resume once concerns about safety, protocol compliance, and data quality are addressed, and satisfy the sponsor, IRB and/or Food and Drug Administration (FDA).

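### If the day-30 call is counted from instillation, SAEs are asked about on schedule for only 9 of the 30 days after the third bronchoscopy

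*Combined protocol and SAP*

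**What the plan says.** Section 8.4.4 sets the recording period for reportable events: from consent "until 7 (for non-serious AEs) or 30 days (for SAEs) after the last day of study research procedure", or until an SAE resolves or stabilises if that is later. It ties active questioning to visits: "At each study visit, the investigator will inquire about the occurrence of AE/SAEs since the last visit". It also says that events "may come to the attention of study personnel during study visits and interviews of a study participant presenting for medical care", or through a study monitor's review. Its telephone and e-mail contact is for the outcome of events already known.

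Section 8.3 adds a web diary, which staff review with the participant at each study visit. A reported possible SAE leads to immediate contact, and participants are told to contact the research nurse with concerns. No closing date for the diary is given.

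Section 4.1 places the final blood and BAL sampling on day 21; the compensation table in 5.6.2 shows visit 6 as day 21 to 22. The last column of the schedule of activities (1.3) is headed "Telephone Follow- up Day 30", and the synopsis gives "Participant Duration: 30 days". No later contact is scheduled anywhere.

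**The concern.** The protocol chooses 30 days after the last procedure as the period in which new SAEs count, but its last scheduled question appears to come well before that period ends. After the call, a new SAE becomes known only if the participant reports it, seeks care in a way that reaches the team, or has a record that a monitor sees. Ascertainment would then be active early in the window and passive later.

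What is at stake is the completeness of the SAE record after the third bronchoscopy. Section 8.4.3.3 says the expected risks come mainly from bronchoscopy and endobronchial manipulation, and lists pneumonitis and pneumothorax without a time limit on onset. All SAEs go to the sponsor and the DSMB (8.4.6). With 20 completers planned, a single unreported SAE would change the safety summary.

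**Working it through.** **Inputs**
- SAE window: 30 days after the last research procedure; non-serious AE window: 7 days (8.4.4).
- Last procedure for a completer: visit 6, nominal day 21 (4.1), or day 22 (5.6.2).
- Last scheduled contact: the call labelled day 30 (1.3).
- Window of −5/+6 days in the schedule. The table is damaged, so applying it to visit 6 is an assumption; it gives day 16 to day 27.
- Bronchoscopy within 2 days after PET-CT (schedule footnote). If the PET-CT moves from day 20 to day 26, bronchoscopy can fall on day 28.

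**Origin of day 30.** From instillation, 30 − 0 = 30 days, which matches the synopsis duration. From the last procedure, the call would fall on day 21 + 30 = 51, which does not match. The label also sits on the same scale as days 0, 4, 5, 20 and 21. The match is supportive but not decisive: the synopsis does not say where its 30 days start, and from a baseline scan 7 days before instillation to a day-30 call is 37 days.

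**Gap, counting the call from instillation**
- End of SAE window = last procedure day + 30.
- Days with no scheduled inquiry = end of window − 30.

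| Last procedure | Window ends | Days after the call | Share of 30 |
|---|---|---|---|
| Day 21 (nominal) | Day 51 | 21 | 70% |
| Day 22 | Day 52 | 22 | 73% |
| Day 16 (−5 days) | Day 46 | 16 | 53% |
| Day 27 (+6 days) | Day 57 | 27 | 90% |
| Day 28 (late PET-CT + 2 days) | Day 58 | 28 | 93% |

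On the nominal schedule the call covers 30 − 21 = 9 days.

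**Early stoppers**, assuming the day-30 call is still made: last procedure on day 20 (PET-CT only) leaves 20 days (67%); on day 5, 5 days (17%); on day 0, none.

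**Non-serious AEs.** Last procedure on day 21 or 22: 21 + 7 = 28 and 22 + 7 = 29, both before the call. The window outlasts the call once the last procedure falls after day 23 (23 + 7 = 30). On day 27 it ends on day 34, 4 days after the call; on day 28 it ends on day 35, 5 days after.

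**If the call is instead counted from the last procedure**, it falls on the last day of the SAE window and the gap is 0 days.

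**The case against.** The strongest objection is that everything depends on one column heading in a damaged table. No body text describes the call or says what it is counted from, and a 30-day call that matches a 30-day window is a conceivable intent. This stands as a condition on the finding. Counting from instillation remains the better reading, for the reasons given in the working.

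A reader might infer that the protocol contradicts itself. It does not. Section 8.4.4 promises to record events that start in the window and promises active inquiry only at visits; a recording window can coexist with passive reporting. The passive routes are also real, since a possible SAE entered in the diary triggers immediate contact.

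A reader might also infer that the stopping rule is undermined, because 10.2 allows suspension for "A single SAE in a subject that is assessed as related or possibly related to the study drug". That rule concerns the study drug. PPD is given once, on day 0, so a day-30 call already gives 30 days of follow-up after the antigen. The 48-hour DSMB notice in 8.4.6 is likewise limited to unexpected SAEs related to the intervention. What remains is mainly late SAEs after a third bronchoscopy done without biopsy (2.3.3).

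Finally, the bronchoscopy effects whose timing is stated in 2.3.1 (sore throat for some hours, fever at six to eight hours) fall within the 9 covered days, and the documents name no risk with onset after that. This limits the priority. It does not explain why the plan sets a 30-day window and then asks about less than a third of it.

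**Conclusion.** The point holds conditionally. If the call is on study day 30 counted from instillation, scheduled SAE inquiry covers the first 9 of the 30 days after the third bronchoscopy, and nominal days 31 to 51 rely on passive routes. The gap is 21 days on schedule and about 16 to 28 days if the visit window and the PET-CT-to-bronchoscopy allowance apply. If visit 6 falls after day 23, the 7-day non-serious window also outlasts the call.

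The 70% figure describes completers on schedule. Section 9.2 says "We will enroll up to an additional 5 subjects in order to achieve 20 completed studies", so it should not be read as applying to all 25 who may be enrolled; those who stop early have a shorter gap or none.

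The number of SAEs that would be missed cannot be estimated from the documents. No efficacy result is affected and antigen follow-up is adequate. Priority is low to moderate: the gap is worth closing because doing so is cheap.

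**What to change.** - Keep the day-30 call, which gives 30 days of follow-up after PPD.
- Add one telephone SAE check 30 days after each participant's actual last research procedure: nominal day 51 for completers (day 46 to 58 across the windows), day 35 for someone whose last procedure was on day 5. For someone who stopped after day 0, the existing call already serves.
- When visit 6 falls after day 23, use the added call to ask also about non-serious events that began within 7 days of it.
- Keep the web diary open until that call and state its closing date.
- State in the schedule of activities what each call is counted from, and align the participant duration in the synopsis (about 51 days from instillation instead of 30).

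If the sponsor confirms that the existing call was always meant to be 30 days after the last procedure, only the wording of the schedule and synopsis needs to change.

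Cost: one call per participant (none for those who stop after day 0), about three weeks longer stated participation, and a protocol amendment with IRB approval and a possible consent update. No visit, sample or procedure is added.

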8.4.5 Adverse Event Reporting

The study investigator will be responsible for reporting all AEs, regardless of attribution, to the sponsor at the time of NIH IRB continuing review and FDA annual report.

If at any time the study investigator believes that a frequency of an AE is greater than anticipated, the investigator will report these findings to the sponsor within 7 days.

8.4.6 Serious Adverse Event Reporting

The study investigator will report to the sponsor any serious adverse event, whether or not considered study intervention related, including those listed in the protocol and must include an assessment of whether there is a reasonable possibility that the study intervention caused the event.

All serious adverse events (SAEs) will be followed until satisfactory resolution or until the investigator deems the event to be chronic or the participant is stable.

The study sponsor will be responsible for notifying the Food and Drug Administration (FDA) of any unexpected fatal or life-threatening suspected adverse reaction as soon as possible, but in no case later than 7 calendar days after the sponsor's initial receipt of the information. In addition, the sponsor must notify FDA and all participating investigators in an Investigational New Drug (IND) safety report of potential serious risks, from clinical trials or any other source, as soon as possible, but in no case later than 15 calendar days after the sponsor determines that the information qualifies for reporting.

All SAEs will be reported to the DSMB at the time of review. However, if an SAE is considered, unexpected and related to the intervention, the study investigator will notify the DSMB of the event within 48 hours.

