8.4.3.3 Expectedness

The principal investigator will be responsible for determining whether an adverse event (AE) is expected or unexpected. An AE will be considered unexpected if the nature, severity, or frequency of the event is not consistent with the risk information previously described for the study intervention. The expected risks will be primarily related to bronchoscopy and endobronchial manipulations. These risks include: dyspnea, cough, sore throat, stridor, wheezing, bronchospasm, hypoxia, laryngeal inflammation, laryngospasm, pneumonitis, pneumothorax, allergic reaction, and anaphylaxis. We expect some vasovagal symptoms during blood draws (expected frequency 50%) and transient bruising at the site of blood draws (expected frequency 50%).

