10.5 SAFETY OVERSIGHT

Safety oversight will be under the direction of a Data and Safety Monitoring Board (DSMB) composed of individuals with the appropriate expertise. Members of the DSMB should be independent from the study conduct and free of conflict of interest, or measures should be in place to minimize perceived conflict of interest. The DSMB will meet at least annually to assess safety and efficacy data on each arm of the study. The DSMB will operate under the rules of an approved charter.

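### A related SAE that is grounds to suspend the study need not reach the DSMB before its next review if the investigator classes it as expected

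*Combined protocol and SAP*

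**What the plan says.** The rules are spread over several sections of the combined protocol and SAP.

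- **Section 8.4.6, default route:** "All SAEs will be reported to the DSMB at the time of review".
- **Section 8.4.6, fast route:** "if an SAE is considered, unexpected and related to the intervention, the study investigator will notify the DSMB of the event within 48 hours". Both conditions must hold.
- **Section 10.5:** the DSMB directs safety oversight under a charter. "The DSMB will meet at least annually to assess safety and efficacy data on each arm of the study".
- **Section 8.4.3.3:** the principal investigator decides expectedness. The test is this: "An AE will be considered unexpected if the nature, severity, or frequency of the event is not consistent with the risk information previously described". The list of expected risks ends with "laryngeal inflammation, laryngospasm, pneumonitis, pneumothorax, allergic reaction, and anaphylaxis", and no grade is attached.
- **Section 6.1.1:** pneumonitis, allergic reaction and anaphylaxis are also named as possible effects of PPD given into the airway.
- **Section 10.2(a):** among the circumstances that may justify suspension or termination is "A single SAE in a subject that is assessed as related or possibly related to the study drug". Expectedness plays no part.
- **Section 10.2, notices and restart:** participants, the IRB and the sponsor are told of a suspension. Resumption must satisfy the sponsor, the IRB and/or the FDA. The DSMB appears in neither list.
- **Section 8.4.3.2:** relatedness has two categories only, Related and Not Related.

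**The concern.** The fast DSMB notice and the suspension criterion use different filters, and the difference falls on the events that matter most here. Pneumonitis and anaphylaxis are named both as plausible effects of the instilled product and as expected risks. If such an event is serious, related and classed as expected, it is grounds to consider stopping the study, yet nothing in the protocol brings it to the DSMB before the next scheduled meeting.

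The participants are healthy volunteers for whom section 2.3.2 claims no direct immediate benefit, and section 6.1.1 notes that the product is indicated only for intradermal use. Suspension is discretionary, so the independent body charged with oversight has most to contribute while that decision is open. As section 10.2 is worded, the study could also be suspended and restarted without the DSMB being told. The statistical section gives no other scheduled look: section 9.4.5 plans no interim analysis, and section 9.4.3 marks safety analyses as not applicable.

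**Working it through.** The plan gives no figure to reproduce, so the check is to run one event through each rule. Take a pneumonitis or anaphylaxis that qualifies as an SAE.

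| Classification | 48-hour DSMB notice (8.4.6) | Criterion 10.2(a) | Latest DSMB notice in the text |
|---|---|---|---|
| Unexpected, related | met | met | 48 hours |
| Expected, related | not met | met | next review |
| Unexpected, possibly related | unclear | met | unclear |
| Expected, possibly related | not met | met | next review |

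Rows 2 and 4 are the gap. Row 3 arises from wording: 8.4.6 says related, 10.2(a) adds possibly related, and 8.4.3.2 has no such category, so the text does not say how a possibly related event is handled under the 48-hour rule.

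**Length of the interval.** Section 10.5 sets a minimum of one meeting a year, so the longest wait in the text is about 12 months, or about 365 days against 2 days under the fast route. This is an upper limit, not a forecast.

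**People challenged in the interval, if the study goes on.** The inputs are 20 completers and up to 25 enrolled (sections 4.1 and 9.2) and a study duration of 5 years (section 1.1). The accrual period is not stated; even accrual is an assumption. Participants per year = number enrolled / accrual years:

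- over 5 years: 20/5 = 4 to 25/5 = 5
- over 3 years: 20/3 = 6.7 to 25/3 = 8.3
- over 2 years: 20/2 = 10 to 25/2 = 12.5

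If the study is suspended at once, the number is zero for as long as the suspension lasts.

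**Chance that the question arises.** The protocol gives no SAE rate. With an assumed risk p of a related SAE per participant, the chance of at least one among n is 1 − (1 − p)^n:

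| Assumed p | n = 20 | n = 25 |
|---|---|---|
| 1% | 18% | 22% |
| 2% | 33% | 40% |
| 5% | 64% | 72% |

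This covers any related SAE. The chance of one that is also classed as expected is no larger, and the documents do not allow it to be estimated.

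**The case against.** The strongest reply is that expectedness is not a matter of looking up a list. Section 8.4.3.3 lets a listed event count as unexpected when its severity or frequency does not fit the risk described. It introduces the list as risks mainly of bronchoscopy and endobronchial manipulation. Section 2.3.1 says that earlier studies of this challenge model reported no serious or unexpected side effects. An investigator could reasonably class a serious anaphylaxis or pneumonitis as unexpected, and the 48-hour notice would follow. This stands, so the gap is possible rather than automatic. It does not close the gap, because the outcome rests on one person's judgement against an ungraded list that names these events.

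Other replies also have force:

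- **Others are told.** The sponsor receives every SAE under 8.4.6, although no deadline is given there. Section 8.4.5 sends an AE frequency above that anticipated to the sponsor within 7 days. On suspension, the IRB and sponsor are told promptly. The events would not go unseen.
- **The charter may cover this.** It is not among the documents and could require earlier notice or an unscheduled review.
- **Different thresholds can coexist.** Section 8.4.6 sets a reporting deadline and 10.2 lists possible grounds for suspension. A reader might infer that the two contradict each other; the difference in filter is a design choice, and only the relatedness wording is inconsistent.

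**Conclusion.** The point holds as a gap in the timing of DSMB notice. Under the protocol's own text, a related SAE classed as expected can be grounds for suspension without reaching the DSMB until its next review, up to about 12 months later. Section 10.2 does not repair this, because the DSMB is neither told of a suspension nor among those to be satisfied before a restart.

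Two stronger readings are tempting and not supported. One is that a related anaphylaxis or pneumonitis SAE must miss the 48-hour notice; section 8.4.3.3 allows it to be classed as unexpected. The other is that about five more people would be challenged before the DSMB hears of it. That count needs the study not to be suspended, the longest permitted interval between meetings, and 25 people enrolled evenly over 5 years.

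The conclusion assumes that the charter sets no earlier notice, which cannot be checked here. This is a cheap improvement in oversight that should be made; it does not affect the validity of the trial's analyses.

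**What to change.** Leave the suspension criterion as it is and change the reporting only.

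1. In section 8.4.6, provide that any SAE meeting 10.2(a) goes to the DSMB within the 48 hours already stated, whether or not it is classed as expected.
2. Reconcile the relatedness wording in 8.4.3.2, 8.4.6 and 10.2, so that it is clear how a possibly related event is recorded and reported. Which scale to use is for the sponsor to decide.
3. In section 8.4.3.3, make clear that being on the expected list does not remove an event from this notice.
4. In section 10.2, add the DSMB to the recipients of a suspension notice, and state what part, if any, it has in resumption.
5. Check the charter, and if it already requires earlier notice, bring the protocol into line with it.

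The cost is wording in four sections and probably a few extra DSMB notices in a study of 20 to 25 people. Visits, procedures and analyses do not change.
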